4 CONCOMITANT MEDICATIONS / MEASURES

4.1 PERMITTED MEDICINES

Any medications (other than those excluded by the clinical trial protocol) that are considered necessary to protect subject welfare and will not interfere with the trial medication may be given at the Investigator's discretion.

4.2 PROHIBITED MEDICINES

The following treatments must not be administered during the trial:

- Immunotherapy including interferon, immunosuppressive drugs (for example, systemic corticosteroids except for short term treatment of allergic reactions, endocrine replacement therapy at low dose prednisone [≤ 10 mg daily] or equivalent, or for the treatment of irAEs or other appropriate short-term steroid use), or other experimental pharmaceutical products. Short term administration of systemic steroid or other immunosuppressant such as infliximab or mycophenolate (that is, for allergic reactions or the management of irAEs) is allowed. Steroids with no or minimal systemic effect (topical, inhalation) are allowed.
- Prophylactic use of corticosteroids for infusion related reactions is prohibited.
- Herbal remedies with immunostimulating properties (for example, mistletoe extract) or known to potentially interfere with major organ function (for example, hypericin).
- Any live vaccine therapies for the prevention of infectious disease. Administration of inactivated vaccines is allowed (for example, inactivated influenza vaccines).

If the administration of a non-permitted concomitant drug becomes necessary during the trial, the subject will be withdrawn from trial treatment.

5 BIOSPECIMEN COLLECTION

5.1. CORRELATIVE STUDIES FOR RESEARCH/PHARMACOKINETIC STUDIES

Studies will address the effect on TGFβ concentrations and other soluble factors in serum and/or plasma upon response to the study drugs, the impact of the somatic genotype on response to M7824 and M9241, and changes in the immune phenotype to predict efficacy of the administered combination immunotherapy. We also will evaluate intratumoral alterations of the immune milieu / stroma of pre- versus post-treatment archival tissues (pre-treatment biopsy and surgical specimen) as well as follow copies of circulating free tumor DNA levels during treatment.

5.1.1 Blood Collection

Blood samples will be originally sent to Blood Processing Core (BPC) for barcoding, initial processing and storage. From this facility coded linked samples will be sent to the designated places for analysis in batch shipments or upon request. Patients will undergo blood and tissue sampling for research purposes on the time points outlined in the Study Calendar [3.8](#)

5.1.2 Tumor and Tissue Collection

Archival tumor samples (collected within 6 months prior to treatment) might be collected at baseline and from the surgical specimen when patients undergo resection.

Test/assay	Volume (approx.)	Type of tube*	Collection point	Location of specimen analysis (and original processing)
PK M7824	Blood, 4 mL	SST	See section 5.1.3	EMD Serono (BPC)
ADA by ELISA	Blood, 4 mL	SST	See Study calendar 3.8	EMD Serono (BPC)
Cytokines by ELISA	Blood, 8 mL	SST	See Study calendar 3.8	EMD Serono (BPC)
TNF by ELISA	Blood, 2x3 mL	Light blue citrate	See Study calendar 3.8	EMD Serono (BPC)
Immune marker panel evaluation by IHC	Archival tumor sample and		Baseline and at surgery	Laboratory of Pathology, NCI

Test/assay	Volume (approx.)	Type of tube*	Collection point	Location of specimen analysis (and original processing)
	surgery sample			
161 DNA-target panel (Oncomine v3 Comprehensive Assay v3)	Archival tumor sample or surgery sample		Baseline or at surgery	[name], Laboratory of Pathology NCI
Circulating free tumor DNA (ctDNA)	Blood, 6 mL	EDTA (purple top) tubes	See Study calendar 3.8	[name], Laboratory of Pathology NCI (BPC)

* Tubes/media may be adjusted at the time of collection based upon materials available and/or to ensure the best viable samples are collected for planned routine and/or research analysis at the time of procedure.

5.1.3 Pharmacokinetic analysis

Only during Phase IA.

PK samples should be taken:

Day -14

M7824 PK: predose, 1h post infusion of M7824 (+/- 15 minutes),

Cycle 1:

M7824 PK: predose, 1h post infusion of M7824 (+/- 15 minutes),

M7824 day 15 predose.

The investigation will be done by EMD Serono under CRADA with this company.

5.1.4 ADA

Anti-Drug Antibody development is an accepted mechanism of loss of efficacy administered human monoclonal antibodies. Measuring titers will ensure that any lack of efficacy of M7824 and/or M9241 is not due to ADA development.

Blood will be collected to analyze ADA according to Study Calendar [3.8](#). Samples positive for ADAs will be re-analyzed to determine the titer. The investigation will be done by EMD Serono using ELISA under CRADA with this company.

5.1.5 Serum cytokines and serum TNF levels

One of the least elaborate ways to confirm that the administered M7824 is active and is engaging its target, is to measure suppression of TGF β levels (via ‘trapping’) and induced changes in the cytokine profile systemically. Following TGF β and cytokine levels longitudinally across treatment course will allow detection of lack of M7824 activity and can trigger additional investigations (ADA development) into lack of efficacy. Initial circulating TGF- β and cytokine levels (including γ -interferon and TNF) will also be tested for correlation with response to M7824 and M9241 or M7824 and M9241 in combination with SBRT therapy overall.

Blood will be collected to analyze soluble factors including cytokines and TNF concentrations according to Study Calendar 3.8. The investigation will be done by EMD Serono using ELISA under CRADA with this company.

5.1.6 Changes in systemic and intratumoral immunogenicity of M7824 and /or M9241 in combination with SBRT (Immune marker panel evaluation by IHC)

Preclinical studies show that TGF β and PD-L1 inhibition and local delivery of rIL-12 cooperate immunologically with RT to induce anti-tumor responses reducing immune evasive cues and enhancing T cell-mediated anti-tumor responses. Immune profiling of pre- and on-treatment specimens including surgical specimens aim to (1) investigate via staining of multiple markers using immunohistochemistry immunogenic cooperativity of M7824 and/or M9241 in combination with RT, and (2) identify an immunologic footprint, either at baseline measure or treatment-induced change, associated with response to the combination approach. This information will also inform on the design of future combination immunotherapy studies. This will be done in the Laboratory of Pathology, NCI.

5.2 SAMPLES FOR GENETIC/GENOMIC ANALYSIS

5.2.1 Description of the scope of genetic/genomic analysis

5.2.1.1 Somatic genomic profile of pancreatic cancers derived from specimens

There is clinical evidence that mutation load drives outcome of immunotherapy in pancreas cancer, and emerging evidence that certain neo-epitopes derived from somatic mutations are more immunogenic than others. For example, it has been postulated that mutations in chromatin-remodeling genes, present in up to 17% of pancreas cancer specimens, or variants affecting the TGF β receptor - SMAD axis, are positively associated with outcome to immunotherapy in cancer. Thus, early correlations between genotype and clinical outcome of patients aim to (1) improve future selection of patients for the dual TGF β ‘trap’ PD-L1 blockade and M9241 immunocytokine therapy in combination with RT approach as well as (2) improve understanding of the mechanism of action of these agents in pancreas cancer which would aid design of future combination therapies.

We will use baseline archival samples as available for somatic tumor variant sequencing which will be performed by the CLIA-approved 50-cancer gene panel of the Molecular Pathology section ([name] lab).

5.2.2 Circulating free tumor DNA measures:

Measures of copies of genomic tumor DNA released into the circulation has been shown to be an accurate measure of tumor burden in patients with solid organ cancers and to have value to follow response to anti-cancer treatment both for the early identification of responders as well as patients

to recur after remission. Including longitudinal measurements from baseline and on-treatment of circulating free tumor DNA into explorative objectives examines the value of identifying responders early and the development of this test as a predictive biomarker for the tested M7824 M9241 combination treatments with SBRT.

We plan to characterize cfDNA from blood before and during treatment. All samples will be subjected to targeted sequencing. This will allow us to characterize somatic point mutations, and copy-number changes and will be performed in [name]'s laboratory.

5.2.3 Management of Results

Subjects will be contacted if a clinically actionable gene variant is discovered. Clinically actionable findings for the purpose of this study are defined as disorders appearing in the American College of Medical Genetics and Genomics recommendations for the return of incidental findings that is current at the time of primary analysis. (A list of current guidelines is maintained on the CCR intranet: <https://ccrod.cancer.gov/confluence/display/CCRCRO/Incidental+Findings+Lists>). Subjects will be contacted at this time with a request to provide a blood sample to be sent to a CLIA certified laboratory.

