5.2.4 Genetic counseling

If the research findings are verified in the CLIA certified lab, the subject will be offered the opportunity to come to NIH (at our expense) to have genetic education and counseling with the NCI Genetics Branch to explain this result. If the subject does not want to come to NIH, a referral to a local genetic healthcare provider will be provided (at their expense). This is the only time during the course of the study that incidental findings will be returned. No interrogations regarding clinically actionable findings will be made after the primary analysis.

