12.4.1.9 Risk of losing data

This includes the risk that data obtained during this study can be released to members of the public, insurers, employers, or law enforcement agencies. Although there are no plans to release results to the patients, family members or health care providers, this risk will be included in the informed consent document

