12.4.1.11 Non-Physical Risks of Genetic Research

Risk of receiving unwanted information

Anxiety and stress may arise as a result of the anticipation that unwanted information regarding disease related DNA sequencing or disease tendencies, or misattributed paternity. Patients will be clearly informed that the data related to DNA sequencing and genetic analysis is coded, investigational and will not be shared with patients, family members or health care providers.

Risk related to possibility that information may be released

This includes the risk that data related to genotype, DNA sequencing or risk for disease tendency or trait can be released to members of the public, insurers, employers, or law enforcement agencies. Although there are no plans to release results to the patients, family members or health care providers, this risk will be included in the informed consent document.

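### Sections 5.2.3–5.2.4 plan to return actionable genetic findings, but Section 12.4.1.11 has patients told that their genetic data stay undisclosed, with no exception

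*Combined protocol and SAP*

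**What the plan says.** Two parts of the combined protocol and SAP deal with what patients learn from their sequencing.

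**The procedure.** Section 5.2.3 states: "Subjects will be contacted if a clinically actionable gene variant is discovered". Actionable is defined narrowly, as "disorders appearing in the American College of Medical Genetics and Genomics recommendations for the return of incidental findings", using the list in force at the primary analysis. Contact consists of a request for blood: "Subjects will be contacted at this time with a request to provide a blood sample to be sent to a CLIA certified laboratory". If that laboratory verifies the finding, Section 5.2.4 offers the patient a visit "to have genetic education and counseling with the NCI Genetics Branch to explain this result", or else a referral to a local genetics provider. Section 5.2.4 describes this step plainly: "This is the only time during the course of the study that incidental findings will be returned".

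**What patients are told.** Section 12.4.1.11, in its paragraph on unwanted information, states: "Patients will be clearly informed that the data related to DNA sequencing and genetic analysis is coded, investigational and will not be shared with patients". The same sentence extends this to family members and health care providers. The next paragraph of 12.4.1.11 says that no release of results is planned. Section 12.4.1.9, which covers loss of study data in general, uses the same sentence: "Although there are no plans to release results to the patients, family members or health care providers".

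**The concern.** One part of the protocol describes a planned return of results. Another describes telling patients that nothing of the kind will be shared. Neither refers to the other, and neither 12.4.1.9 nor 12.4.1.11 carves out the actionable findings of 5.2.3.

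Participant information is what is at stake. The statement in 12.4.1.11 is offered as the answer to the risk of receiving unwanted genetic information. Section 5.2.3 creates that risk, because a patient may be approached, unprompted, about a disorder on the incidental-findings list. Sections 5.2.3 and 5.2.4 do not mention asking patients beforehand whether they want to be approached. A patient told what 12.4.1.11 describes would have no reason to expect the contact.

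**Working it through.** The plan gives no figure on this point and no arithmetic applies. The check sets the statements side by side.

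| Question | Sections 5.2.3–5.2.4 | Sections 12.4.1.9 and 12.4.1.11 |
|---|---|---|
| Is a patient approached because of a research sequencing result? | Yes, when an actionable variant is found | Not mentioned; 12.4.1.11 says the data are not shared with patients |
| Is a result explained to the patient? | Yes, after certified-laboratory verification, with counseling | No release of results is planned |
| Is a provider outside the study involved? | Yes, by referral if the patient prefers not to travel | 12.4.1.11 says the data are not shared with health care providers |
| Is an exception or cross-reference given? | None to 12.4.1.9 or 12.4.1.11 | None to 5.2.3 or 5.2.4 |

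**Step 1: is there a planned return?** Yes. Section 5.2.4 itself says that incidental findings will be returned at this step.

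**Step 2: are the statements in Section 12 qualified?** No. Section 12.4.1.11 covers sequencing and genetic data without limit. The no-release sentence, there and in 12.4.1.9, refers to results without limit.

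**Step 3: does the laboratory confirmation step separate the two?** Only in part. Under 5.2.3 the trigger for contact is discovery of the variant in the research sequencing. The confirmatory sample is requested afterwards. The request itself therefore tells the patient that the research data showed something, before any certified result exists.

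**Step 4: how many patients are concerned?** Section 5.2.2 has all cfDNA samples sequenced, and the study calendar (Section 3.8) schedules a cfDNA sample at baseline. Archival tumor is sequenced as available (Section 5.2.1.1). The information in 12.4.1.11 thus bears on essentially every participant, up to the accrual ceiling of 52 in Section 10.2. Only those with a variant on the list would be contacted. The documents give no rate from which to estimate that number.

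**The case against.** The best defense is that the two parts describe different things. Section 12.4.1.11 speaks of coded, investigational data, whereas 5.2.3–5.2.4 call for a new blood sample and return only what a certified laboratory verifies. Withholding research data while returning verified findings is a coherent policy, and may well be what the sponsor intends. This stands to the extent that the two parts can be reconciled by stating an exception. It does not remove the conflict, because the text does not state that exception and contact comes before verification.

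It is also fair that 12.4.1.9 is weaker support. That section is mainly about release to the public, insurers, employers or law enforcement, and does not mention genetic findings. Its no-release sentence is nevertheless unqualified.

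A reader might infer three stronger things that the documents do not support.

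- *The consent form misstates the trial.* The consent pages are not in the review copy. The form may already describe the 5.2.3 procedure.
- *Actionable findings will be withheld.* Nothing shows this. Sections 5.2.3–5.2.4 commit to returning them, and the gap is in how this is described to patients.
- *Return would come so late that few patients could benefit.* This requires the primary analysis named in 5.2.3–5.2.4 to be the trial's own. The term is undefined there and can equally mean the first analysis of the patient's sample. Any estimate of the fraction still alive would also need an assumed time to analysis and a choice of median survival. The documents' medians range from about 9 months (Section 12.4.3) to 18–20 months in several series in Table 3.

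**Conclusion.** The inconsistency is real and lies in the current text. Sections 5.2.3–5.2.4 plan to contact patients and return verified actionable findings. Section 12.4.1.11, supported by the general sentence in 12.4.1.9, has patients told otherwise, without exception. Patients informed as 12.4.1.11 describes would be misinformed about a planned procedure and about the risk of an unsolicited approach.

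The conclusion rests on the protocol wording alone and assumes nothing about the consent form. It concerns what essentially all participants are told, although the number contacted may be small. It has no bearing on the response-rate design, the error rates, the sample size or the primary analysis. It should be corrected because participants rely on the information and the correction is simple.

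**What to change.** 1. In 12.4.1.11, and in the matching sentence of 12.4.1.9, state that research sequencing results are not returned, with one exception: patients with an actionable finding under 5.2.3 will be contacted for a confirmatory sample and offered the result once a CLIA laboratory has verified it.
2. In the 12.4.1.11 paragraph on unwanted information, list that contact as a risk.
3. Check the consent form against 5.2.3–5.2.4 and align it if it repeats the unqualified statement.
4. Optionally, define the primary analysis named in 5.2.3–5.2.4 as either the first analysis of the patient's sample or the trial's primary analysis. No particular timing of contact is urged here.

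The cost is a wording amendment. Confirmation, counseling and referral are already planned, so no new procedure is needed. If the consent form has to change, the Statement of Compliance already requires IRB approval and an IRB determination on whether enrolled participants need to consent again.

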5.2.4 Genetic counseling

If the research findings are verified in the CLIA certified lab, the subject will be offered the opportunity to come to NIH (at our expense) to have genetic education and counseling with the NCI Genetics Branch to explain this result. If the subject does not want to come to NIH, a referral to a local genetic healthcare provider will be provided (at their expense). This is the only time during the course of the study that incidental findings will be returned. No interrogations regarding clinically actionable findings will be made after the primary analysis.

5.3 SAMPLE STORAGE, TRACKING AND DISPOSITION

Samples will be ordered in CRIS and tracked through a Clinical Trial Data Management system. Should a CRIS screen not be available, the CRIS downtime procedures will be followed. Samples will not be sent outside the National Institutes for Health (NIH) without appropriate approvals and/or agreements, if required.

All samples will be barcoded, with data entered and stored in the secure databases. These databases create a unique barcode ID for every sample and sample box, which cannot be traced back to patients without database access. The data recorded for each sample includes the patient ID, name, trial name/protocol number, time drawn, cycle time point, dose, material type, as well as box and freezer location. Patient demographics associated with the clinical center patient number are provided in the system. For each sample, there are notes associated with the processing method (delay in sample processing, storage conditions on the ward, etc.).

Barcoded samples are stored in barcoded boxes in a locked freezer at either -20 or -80°C according to stability requirements.

Access to stored clinical samples is restricted. Samples will be stored until requested by a researcher named on the protocol. All requests are monitored and tracked in database. All researchers are required to sign a form stating that the samples are only to be used for research purposes associated with this trial (as per the IRB approved protocol) and that any unused samples must be returned. It is the responsibility of the NCI Principal Investigator to ensure that the samples requested are being used in a manner consistent with IRB approval.

5.3.1 Protocol Completion/Sample Destruction

All specimens obtained in the protocol are used as defined in the protocol. Any specimens that are remaining at the completion of the protocol will be stored in the conditions described in sections above. The study will remain open so long as sample or data analysis continues. Samples from consenting subjects will be stored until they are no longer of scientific value or if a subject withdraws consent for their continued use, at which time they will be destroyed. The PI will record any loss or unanticipated destruction of samples as a deviation. Reports will be made per the requirements of section [7.2](#).

If the patient withdraws consent the participant's data will be excluded from future distributions, but data that have already been distributed for approved research use will not be able to be retrieved.

6 DATA COLLECTION AND EVALUATION

6.1 DATA COLLECTION

The PI will be responsible for overseeing entry of data into an in-house password protected electronic system (C3D) and Labmatrix ensuring data accuracy, consistency and timeliness. The principal investigator, associate investigators/research nurses and/or data manager will assist with the data management efforts. Primary and final analyzed data will have identifiers so that research data can be attributed to an individual human subject participant.

All adverse events, including clinically significant abnormal findings on laboratory evaluations, regardless of severity, will be followed until return to baseline or stabilization of event.

Document AEs from the administration of the first study intervention through 28 days after the last study agent (s) is administered. Beyond 28 days after the last intervention, only adverse events which are serious and related to the study intervention need to be recorded.

An abnormal laboratory value will be recorded in the database as an AE only if the laboratory abnormality is characterized by any of the following:

- Results in discontinuation from the study
- Is associated with clinical signs or symptoms
- Requires treatment or any other therapeutic intervention
- Is associated with death or another serious adverse event, including hospitalization.
- Is judged by the Investigator to be of significant clinical impact

- If any abnormal laboratory result is considered clinically significant, the investigator will provide details about the action taken with respect to the test drug and about the patient's outcome.

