The safety of the above treatment scheme has also been reported by other institutions. A retrospective review from the Moffitt Cancer Center analyzed 73 patients with LAPC or borderline resectable pancreatic cancer who underwent chemotherapy followed by SBRT to a dose of 35 Gy to the area of vessel involvement and 25 Gy to the remaining tumor over 5 fractions.[67] Thirty one of 32 patients with borderline resectable cancer achieved an R0 resection. Median overall survival at 1 year for borderline resectable versus LAPC patients was 16.4 versus 15 months. Those patients with borderline resectable lesions who attained R0 resection had improved median overall survival as compared with nonsurgical patients, although 1-year local control in nonsurgical patients was 81%. There was no grade 3 or greater acute toxicities. Four patients were noted to have late grade 3 toxicities (3 with GI bleeding requiring embolization and 1 with anorexia resulting in feeding tube placement). It is important to note that toxicities due to RT cannot infrequently occur in a delayed fashion; for example, in of the largest retrospective reviews on SBRT in LAPC median time to grade 2 to 4 toxicities was 6.3 months. At 6 months, the actuarial rate of toxicity was 11%, and at 12 months, this rose to 29%. [68]

The optimum sequence of immune-oncology agents and RT has not been established. We have elected to start M7824 and M9241 2 weeks prior to SBRT because of maximal MHC expression and tumor antigen presentation that is changed by radiation happens within 48-72 hours after radiation. While cross-presented antigen, upregulated by cGAS/STING/dsDNA-related

mechanisms, and dsDNA released by the irradiated and dying but not-yet-disappeared cells can in many tumors persist for very long periods of time as they march towards eventual mitotic catastrophe, giving the immunomodulating agents upfront priming the microenvironment towards antigen recognition and CD8 T cell response appears to have the highest likelihood of exploiting all RT-induced changes which might not be synchronous for immunogenic synergy. Administering the M7824 and M9241 beginning 2 weeks prior to SBRT allows for the delivery of radiation shortly after M7824 and M9241 have been introduced, with M7824 and M9241 continuing during and after the radiation, so that the predicted peak period of antigenicity following radiation coincides with activity of the immunomodulatory agents.

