¹⁴ A Safety Follow-up visit is scheduled 4 weeks (28 ± 5 days) after the last administration of M7824 or M9241 but before any new therapy is started, if possible, whichever occurs earlier. All SAEs ongoing at the 28-Day Safety Follow-up visit must be monitored and followed up by the Investigator until stabilization or until the outcome is known, unless the subject is documented as “lost to follow-up.” In addition, all trial drug-related SAEs occurring after 28 Day Safety Follow up visit and ongoing at the Safety Follow-up visit have to be followed up in the same manner

¹⁵ Subjects with PD will be followed every 12 weeks (± 2 weeks) by phone or e-mail for survival and further tumor therapy for 1 year after the last dose of study drug. After 1-year subjects will be followed for survival every 6 month. Subjects without progressive disease at 28-Day Safety Follow-up visit will be invited to Clinical Center to perform CT scans (or MRI scans if clinically indicated) every 12 weeks (± 2 weeks) until PD. Outside scans are acceptable.

¹⁶ If subjects are not willing to come to NIH after treatment discontinuation for FU visits, they will be followed by phone call or e-mail.

¹⁷ Must be done before re-treatment after surgery.

¹⁸ Every 6 weeks

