8.1.5 Relationship to Study Product

All AEs will have their relationship to study product assessed using the terms: related or not related.

- Related – There is a reasonable possibility that the study product caused the adverse event. Reasonable possibility means that there is evidence to suggest a causal relationship between the study product and the adverse event.
- Not Related – There is not a reasonable possibility that the administration of the study product caused the event.

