8.2 ASSESSMENT OF SAFETY EVENTS

AE information collected will include event description, date of onset, assessment of severity and relationship to study product and alternate etiology (if not related to study product), date of resolution of the event, seriousness and outcome. The assessment of severity and relationship to the study product will be done only by those with the training and authority to make a diagnosis and listed on the Form FDA 1572 as the site principal investigator or sub-investigator. AEs occurring during the collection and reporting period will be documented appropriately regardless of relationship. AEs will be followed through resolution.

SAEs will be:

- Assessed for severity and relationship to study product and alternate etiology (if not related to study product) by a licensed study physician listed on the Form FDA 1572 as the site principal investigator or sub-investigator.
- Recorded on the appropriate SAE report form, the medical record and captured in the clinical database.
- Followed through resolution by a licensed study physician listed on the Form FDA 1572 as the site principal investigator or sub-investigator.

For timeframe of recording adverse events, please refer to section [6.1](#). All serious adverse events recorded from the time of first investigational product administration must be reported to the Sponsor with the exception of any listed in section [8.4](#).

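### Adverse event recording is timed from the last drug dose, so late non-serious SBRT toxicity may go unrecorded in patients who stop the drugs early

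*Combined protocol and SAP*

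**What the plan says.** Section 6.1 sets the general window: "Document AEs from the administration of the first study intervention through 28 days after the last study agent (s) is administered". After that, "only adverse events which are serious and related to the study intervention need to be recorded". Section 8.2 defers to the same rule ("For timeframe of recording adverse events, please refer to section" 6.1), and no section sets a window counted from SBRT.

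Sections 3.1 and 3.3.3 give SBRT once, starting on Day 17 (+5 days) of Cycle 1, over five business days. The drugs then continue until an off-treatment criterion in Section 3.11.1 is met; these include progression, excessive toxicity and successful tumor removal.

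Section 1.2.7 describes delayed toxicity in one large retrospective review: "median time to grade 2 to 4 toxicities was 6.3 months", and "At 6 months, the actuarial rate of toxicity was 11%, and at 12 months, this rose to 29" (per cent). In a second series, of 73 patients: "Four patients were noted to have late grade 3 toxicities".

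On attribution, Section 8.1.5 says: "All AEs will have their relationship to study product assessed using the terms: related or not related". Section 6.1 speaks instead of the study intervention, and footnote 14 of the calendar in Section 3.8 speaks of SAEs related to trial drug.

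The calendar marks adverse events at long-term follow-up. Footnote 15 has patients with progression contacted every 12 weeks "by phone or e-mail for survival and further tumor therapy for 1 year after the last dose of study drug", and patients without progression scanned every 12 weeks.

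**The concern.** The first primary objective is the safety of the two drugs given with SBRT, and Section 10.1.1 measures it by treatment-related adverse events of the whole combination. The recording clock, however, follows the drugs, while the radiation hazard described in Section 1.2.7 runs from SBRT. A patient who stops the drugs after a few cycles leaves the general window before most of the cited toxicity would appear.

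The dose-limiting toxicity period does not fill this gap. In Phase IB it ends on Day 28 of Cycle 1. SBRT starts between Day 17 and Day 22 and, barring holidays, its last fraction falls between Day 21 and Day 28, which leaves 0 to 7 days of observation.

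Resected patients matter most here. They stop the drugs, and in the gemcitabine chemoradiation series in Section 1.2.1 they lived longest (median 34 months, against 7 months without surgery), so they have the most time at risk of late toxicity.

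**Working it through.** **Inputs.** Toxicity: 11% at 6 months and 29% at 12 months (Section 1.2.7; literature figures that cannot be recomputed from the documents). Window: last dose + 28 days (Section 6.1). SBRT start: Day 17 (Section 3.1). Median overall survival: 9 months (Section 12.4.3). Phase II size, for scale: 25 (Section 10.2). Assumptions: time on drug after SBRT, and an alternative median survival of 18 months (the two largest series in Table 3 report 18.1 and 18.4 months).

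**Step 1. Timing of the cited toxicity.** (29 − 11)/29 = 62% of the 12-month toxicity arises after month 6.

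**Step 2. When the window closes.** Days after SBRT start = last dose day + 28 − 17. To reach 6 months (182.6 days) the last dose must be on Day 172 or later (Cycle 7); to reach 12 months (365.25 days), on about Day 354 or later (Cycle 13). Interpolating the cited curve for a patient alive throughout:

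| Last dose | Window closes, months after SBRT start | Share of 12-month toxicity after closing |
|---|---|---|
| Cycle 3 Day 15 | 2.7 | 82–83% |
| Cycle 6 Day 15 | 5.5 | 65–66% |
| Cycle 9 Day 15 | 8.2 | 38–39% |
| Cycle 12 Day 15 | 11.0 | 10–11% |
| Cycle 13 Day 15 | 11.9 | about 1% |

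Each range spans linear and piecewise-exponential interpolation.

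**Step 3. Average over patients, with death.** Monthly toxicity hazards are −ln(0.89)/6 = 0.0194 up to month 6 and −ln(0.71/0.89)/6 = 0.0377 from month 6 to 12, giving a density f(t). Drug time after SBRT is exponential with rate a = ln 2/median. Survival after drug stop is exponential with rate b, chosen so that drug time plus residual survival has the stated median. With w = 28 days = 0.92 months,

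P(window closed and alive at t) = a·exp(−bt)·[1 − exp(−(a − b)(t − w))]/(a − b), for t > w,

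and the toxicity falling after the window is the integral of f(t) times this probability from 0 to 12 months. Example: drug median 3 months and survival median 9 give a = 0.231, a residual median of 4.5 months, b = 0.154, and a result of 8.7 points.

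| Median drug time (months) | Ignoring death | Median survival 9 | Median survival 18 |
|---|---|---|---|
| 3 | 18.7 points | 8.7 | 14.1 |
| 4 | 16.3 | 6.4 | 12.0 |
| 6 | 12.9 | 2.9 | 8.8 |
| 9 | 9.7 | not possible | 5.7 |
| 12 | 7.8 | not possible | 3.5 |

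Time on drug cannot exceed survival, so a drug median of 9 months or more does not fit a survival median of 9. As shares of the toxicity that occurs before death, the 9-month column is 46%, 34% and 16%, and the 18-month column runs from 58% to 14%. In 25 patients, 2.9 to 8.7 points is 0.7 to 2.2 patients, and 3.5 to 14.1 points is 0.9 to 3.5 patients.

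**The case against.** Several points on the other side stand.

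- The cited rates may not transfer. Section 1.2.7 gives no dose for that review, and Table 4 shows how widely SBRT schedules differ (BED at alpha/beta 3 of 67 for 5 Gy x 5 and 233 for 25 Gy x 1). The series reported in support of the trial's scheme had 4 late grade 3 events in 73 patients (5.5%): three bleeds needing embolization and one feeding tube. Such events would plausibly count as serious and, if judged related, would still be recorded.
- Events that begin inside the window are followed to resolution or stabilization (Sections 6.1 and 8.2). Section 6.3.3 expects patients with response or stable disease to be treated through 24 months, so their window covers the late period.
- The recommended dose rests on the 28-day toxicity period, the adverse event analysis is descriptive, and no late-toxicity endpoint is planned. The gap changes no decision rule.

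A reader might infer from Section 8.1.5 that late events blamed on SBRT will be called unrelated and discarded. The documents do not establish this. The governing sentence in 6.1 refers to the study intervention, and Sections 3.1.2, 3.2 and 3.4 attribute events to SBRT or to the regimen. The narrower terms in 8.1.5 and footnote 14 make such a loss possible, so the wording should be aligned. Nor is the calendar's long-term mark a clear contradiction: it may simply serve the serious related events that 6.1 keeps.

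None of this supplies a place to record a non-serious grade 2 or 3 radiation event that begins after the window closes.

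**Conclusion.** The point holds as a gap in data collection. Late non-serious SBRT toxicity may be missed in patients who stop the drugs well before 12 months after SBRT, and the primary safety description is truncated to that extent.

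Its illustrative size is about 3 to 9 percentage points with median survival of 9 months and median drug time of 3 to 6 months, or about 4 to 14 points with median survival of 18 months and drug times of 3 to 12 months. These figures assume that the cited 11% and 29% apply, that drug time and residual survival are exponential, and that toxicity is independent of both. They are upper bounds, because serious related events remain recordable and the documents do not give that share.

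A reader might take the 62% from Step 1, or the 8 to 19 points obtained when death is ignored, as the expected loss. Neither is supported: the first presumes that everyone stops drug early, and the second counts toxicity in patients who would already have died. The documents support *may be missed in early stoppers*, not a general statement that late toxicity will be under-reported.

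**What to change.** - In Section 6.1, for Cohorts 2 and 3, record grade 2 or higher gastrointestinal, hepatobiliary and bleeding events until 12 months after SBRT, serious or not, at the existing 12-weekly contacts or scans.
- State that study intervention includes SBRT, and add to Section 8.1.5 a relationship assessment for SBRT separate from that for the drugs.
- Bring the calendar's long-term adverse event mark and footnotes 14 and 15 into line with this.
- Report 6- and 12-month cumulative incidence descriptively, with death as a competing event.

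The cost is one short form at contacts already planned; no procedure is added and patient management does not change. The drawbacks are real: grading by phone is less exact, later therapy or surgery blurs attribution, and about 25 patients give low precision. If the sponsor prefers not to extend recording, the protocol should state that late SBRT toxicity is reported for serious related events only.
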